7.1.2. Recording and Reporting Adverse Events

For adverse event recording, the study period is defined for each patient as that time period from signature of the informed consent form through the end of the study.

All adverse events that occur during the defined study period must be recorded on the source documentation and transcribed onto the CRF, regardless of the severity of the event or judged relationship to the study drug. For SAEs, the SAE Form must also be completed and the SAE must be reported immediately (see Section 7.1.5.3.1). The investigator does not need to actively monitor patients for adverse events once the study has ended. Serious adverse events occurring to a patient after the treatment of that patient has ended should be reported to the sponsor if the investigator becomes aware of them, following the procedures described in Section 7.1.5.3.1.

At each contact with the patient, the investigator or designee must question the patient about adverse events by asking an open-ended question such as, "Have you had any unusual symptoms or medical problems since the last visit? If yes, please describe." All reported or observed signs and symptoms will be recorded individually, except when considered manifestations of a medical condition or disease state. A precise diagnosis will be recorded whenever possible. When such a diagnosis is made, all related signs, symptoms, and any test findings will be recorded collectively as a single diagnosis on the CRF and, if it is a SAE, on the SAE Form.

The clinical course of each adverse event will be monitored at suitable intervals until resolved or stabilized or returned to baseline, or until the patient is referred for continued care to a another health care professional, or until a determination of a cause unrelated to the study drug or study procedure is made.

The onset and end dates, duration (in case of adverse event duration of less than 24 hours), action taken regarding study drug, treatment administered, and outcome for each adverse event must be recorded on the source documentation and transcribed onto the CRF.

The relationship of each adverse event to study drug treatment and study procedures, and the severity and seriousness of each adverse event, as judged by the investigator, must be recorded as described below.

7.1.3. Severity of an Adverse Event

The severity of each adverse event must be recorded as 1 of the choices on the following scale:

- Mild:** No limitation of usual activities
- Moderate:** Some limitation of usual activities
- Severe:** Inability to carry out usual activities

7.1.4. Relationship of an Adverse Event to the Study Drug

The relationship of an adverse event to the study drug is characterized as follows:

Term	Definition	Clarification
No reasonable possibility (not related)	This category applies to adverse events that, after careful consideration, are clearly due to extraneous causes (disease, environment, etc) or to adverse events that, after careful medical consideration at the time they are evaluated, are judged to be unrelated to the study drug.	The relationship of an adverse event may be considered “no reasonable possibility” if it is clearly due to extraneous causes or if at least 2 of the following apply: 
 • It does not follow a reasonable temporal sequence from the administration of the study drug. • It could readily have been produced by the patient’s clinical state, environmental, or toxic factors, or other modes of therapy administered to the patient. • It does not follow a known pattern of response to the study drug. • It does not reappear or worsen when the study drug is re-administered.
Reasonable possibility (related)	This category applies to adverse events for which, after careful medical consideration at the time they are evaluated, a connection with the study drug administration cannot be ruled out with certainty.	The relationship of an adverse event may be considered “reasonable possibility” if at least 2 of the following apply: 
 • It follows a reasonable temporal sequence from administration of the study drug. • It cannot be reasonably explained by the known characteristics of the patient’s clinical state, environmental or toxic factors or other modes of therapy administered to the patient. • It disappears or decreases on cessation or reduction in dose. There are important exceptions when an adverse event does not disappear upon discontinuation of the study drug, yet a drug relationship clearly exists. • It follows a known pattern of response to the study drug.

7.1.5. Serious Adverse Events

7.1.5.1. Definition of a Serious Adverse Event

A SAE is an adverse event occurring at any dose that results in any of the following outcomes or actions:

- death
- a life-threatening adverse event (i.e., the patient was at immediate risk of death from the event as it occurred); does not include an event that, had it occurred in a more severe form, might have caused death
- inpatient hospitalization or prolongation of existing hospitalization, which means that hospital inpatient admission and/or prolongation of hospital stay were required for treatment of an adverse event, or that they occurred as a consequence of the event. Hospitalizations scheduled prior to study entry will not be considered SAEs, unless

there was worsening of the preexisting condition during the patient's participation in this study.

- persistent or significant disability or incapacity (refers to a substantial disruption of one's ability to conduct normal life functions)
- a congenital anomaly/birth defect
- an important medical event that may not result in death, be life-threatening, or require hospitalization, but may jeopardize the patient and may require medical intervention to prevent one of the outcomes listed in this definition. Examples of such events are intensive treatment in an emergency room or at home for allergic bronchospasm; blood dyscrasias or convulsions that do not result in hospitalization; or the development of drug dependency or drug abuse. Note: Any suspected transmission of an infectious agent via a medicinal product is considered an important medical event.

An adverse event that does not meet any of the criteria for seriousness listed above will be regarded as a nonserious adverse event.

7.1.5.2. Expectedness

A SAE that is not included in the Adverse Reaction section of the relevant reference safety information by its specificity, severity, outcome, or frequency is considered an unexpected adverse event. The reference safety information for this study is the IB.

A SAE that is not included in the Listing of Adverse Reactions in the IB by its specificity, severity, outcome, or frequency is considered an unexpected adverse event.

The sponsor's Pharmacovigilance Department will determine the expectedness for all SAEs.

For the purpose of suspected unexpected serious adverse reaction (SUSAR)/IND safety reporting, the version of the reference safety information (RSI) at the moment of occurrence of the SUSAR/IND safety report applies.

7.1.5.3. Reporting a Serious Adverse Event

7.1.5.3.1. Investigator Responsibility

To satisfy regulatory requirements, all SAEs (as described in Section 7.1.5.1) that occur during the study period (including the protocol-defined follow-up period, described in Section 7.1.2), regardless of judged relationship to treatment with the study drug, must be reported to the sponsor by the investigator. The event must be reported within 24 hours of when the investigator learns about it. Completing the SAE form and reporting the event must not be delayed, even if not all the information is available. The investigator does not need to actively monitor patients for adverse events once this study has ended. Serious adverse events occurring to a patient after the treatment of that patient has ended should be reported to the sponsor if the investigator becomes aware of them.

The SAE form should be sent to the LSO or other designated personnel (a contract research organization [CRO] in a country without a sponsor LSO) (contact information is in the Clinical Study Personnel Contact Information section); the LSO or other designated personnel will forward the report to the sponsor's Global Patient Safety & Pharmacovigilance Department.

The following information should be provided to record the event accurately and completely:

- Study number
- investigator and investigational center identification
- patient number
- onset date and detailed description of adverse event
- investigator's assessment of the relationship of the adverse event to the study drug (no reasonable possibility, reasonable possibility)

Additional information may include the following:

- age and sex of patient
- date of first dose of study drug
- date and amount of last administered dose of study drug
- action taken
- outcome, if known
- severity
- explanation of assessment of relatedness
- concomitant therapy (including doses, routes, and regimens) and treatment of the event
- pertinent laboratory or other diagnostic test data
- medical history
- results of dechallenge/rechallenge, if known
- for an adverse event resulting in death:
 - cause of death (whether or not the death was related to study drug)
 - autopsy findings (if available)

Each report of a SAE will be reviewed and evaluated by the investigator and the sponsor to assess the nature of the event and the relationship of the event to the study drug, study procedures, and to underlying disease.

Additional information (follow-up) about any SAE unavailable at the initial reporting should be forwarded by the investigational center within 24 hours of when it becomes known to the same address as the initial report.

For all countries, the sponsor's Global Patient Safety & Pharmacovigilance Department will distribute the Council for International Organizations of Medical Sciences (CIOMS) form/XML file to the LSO/CRO for local submission to the regulatory authorities, IEC/IRBs, and investigators, according to regulations. The investigator is responsible for ensuring that the IRB/EC is also informed of the event, in accordance with local regulations.

Note: Although pregnancy is not a SAE, the process for reporting a pregnancy is the same as that for reporting a SAE, but using the pregnancy form (see Section 7.2).

7.1.5.3.2. Sponsor Responsibility

If a serious unexpected adverse event is believed to be related to the study drug or study procedures, the sponsor will take appropriate steps to notify all investigators participating in sponsored clinical studies of pridopidine and the appropriate regulatory authorities (and IEC/IRB, if appropriate).

In addition to notifying the investigators and regulatory authorities (and IEC/IRB, if appropriate), other measures may be required, including the following:

- altering existing research by modifying the protocol
- discontinuing or suspending the study
- altering the process of informed consent by modifying the existing consent form and informing current study participants of new findings
- modifying listings of expected toxicities to include adverse events newly identified as related to pridopidine

7.1.6. Protocol-Defined Adverse Events for Expedited Reporting

Adverse events of suicidal ideations or attempt should be reported to the sponsor within 24 hours of learning of the event. The corresponding dedicated CRF should be completed, but the events should not be marked as serious unless deemed serious by the investigator. The words "protocol defined adverse event" should be added after the adverse event term. Once the adverse event of suicidal ideation or attempt is received, the patient should be discontinued from the study and from study medication, and referred to a psychiatrist for evaluation and monitoring (see Section 7.1.7).

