7.1. Adverse Events

7.1.1. Definition of an Adverse Event

An adverse event is any untoward medical occurrence in a patient administered a pharmaceutical product, regardless of whether it has a causal relationship with this treatment.

In this study, any adverse event occurring after the clinical study patient has signed the informed consent form should be recorded and reported as an adverse event.

An adverse event can, therefore, be any unfavorable and unintended physical sign, symptom, or laboratory parameter that develops or worsens in severity during the course of this study, or significant worsening of the disease under study or of any concurrent disease, whether or not considered related to the study drug. A new condition or the worsening of a pre-existing condition will be considered an adverse event. Stable chronic conditions (such as arthritis) that are present before study entry and do not worsen during this study will not be considered adverse events.

New symptoms of HD or deterioration of previously existing symptoms should be recorded as an AE only if the presentation and/or outcome is more severe than would normally be expected from the normal course of the disease in a particular patient.

In any event of suspected suicidality or clinical findings suggesting that the patient is dangerous to him or herself at the moment of evaluation or during the duration of the clinical study, the patient should be discontinued from treatment with study drug, referred for **immediate** psychiatric evaluation and an AE/SAE should be reported. Patients with an AE/SAE of suicide ideation or attempt will be discontinued from treatment with study drug. Patients who are discontinued from treatment may continue their participation in the study and perform the scheduled visits and assessments, while off study drug.

Accordingly, an adverse event can include any of the following:

- intercurrent illnesses
- physical injuries
- events possibly related to concomitant medication
- significant worsening (change in nature, severity, or frequency) of the disease under study or other pre-existing conditions (Note: A condition recorded as pre-existing that is intermittently symptomatic [eg, headache] and that occurs during this study should be recorded as an adverse event.)
- drug interactions

- events occurring during diagnostic procedures or during any washout phase of this study

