7.1.7. Withdrawal Due to an Adverse Event

Any patient who experiences an adverse event may be withdrawn from the study or from study treatment at any time at the discretion of the investigator. If a patient is withdrawn wholly or in part because of an adverse event, both the adverse events page and termination page of the CRF will be completed at that time.

In addition, a blood sample will be aimed to be obtained, to the extent possible, for the measurement of study drug concentrations. The patient will be monitored at the discretion of the investigator (eg, until the event has resolved or stabilized, until the patient is referred to the care of a health care professional, or until a determination of a cause unrelated to the study drug or study procedure is made). The investigator must inform the Medical Monitor as soon as possible of all patients who are being considered for withdrawal due to adverse events. Additional reports must be provided when requested.

If a patient is withdrawn from the study for multiple reasons that include adverse events, the termination page of the CRF should indicate that the withdrawal was related to an adverse event. An exception to this requirement will be the occurrence of an adverse event that in the opinion of the investigator is not severe enough to warrant discontinuation but that requires the use of a

prohibited medication, thereby requiring discontinuation of the patient. In such a case, the reason for discontinuation would be need to take a prohibited medication, not the adverse event.

All patients for whom an adverse event of suicidal behavior/ideation was reported at any time during the study should be discontinued from study medication and the need for an evaluation by a psychiatrist should be assessed. Discontinued patients should attend an early termination visit to return study medication, perform drug accountability, and will be asked to complete all protocol required study procedures. Adverse events of suicidal behavior/ideation should be followed until resolution of the suicidal behavior/ideation.

All patients who are discontinued from the study medication due to active suicidal behavior/ideation should be referred to a psychiatrist and followed by the investigator until resolution of the suicidal behavior/ideation.

Patients who discontinue study medication due to safety or tolerability reasons may continue in the study off drug and perform the scheduled visits and assessments.

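### Protocol 7.1.6 takes a patient with an adverse event of suicidal ideation or attempt out of the study, other sections stop drug only, and the tolerability endpoints count leaving the study

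*Protocol*

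**What the plan says.** Protocol 7.1.6 covers expedited reporting of adverse events of suicidal ideation or attempt. Once such an event is received, it says, "the patient should be discontinued from the study and from study medication, and referred to a psychiatrist for evaluation and monitoring", and it points to 7.1.7.

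Protocol 7.1.1 has a different rule for the same event: "Patients with an AE/SAE of suicide ideation or attempt will be discontinued from treatment with study drug". It adds: "Patients who are discontinued from treatment may continue their participation in the study and perform the scheduled visits and assessments, while off study drug".

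Protocol 7.1.7 says that patients with a reported event of this kind "should be discontinued from study medication and the need for an evaluation by a psychiatrist should be assessed". It then states: "Discontinued patients should attend an early termination visit to return study medication". That sentence goes on to ask for drug accountability and for completion of the procedures the protocol requires. The section closes with: "Patients who discontinue study medication due to safety or tolerability reasons may continue in the study off drug".

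Protocol 3.10.1 lists this event among the reasons to discontinue a patient, without saying whether drug or study is meant. The list comes after a QTcF rule that withdraws the patient from the study. The section then also allows patients who stop drug for safety or tolerability to stay.

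The two tolerability endpoints (Protocol 2.3.1.2 and 9.8.1, SAP 1.2.2) are the proportions who prematurely discontinue the study, for any reason and because of adverse events. SAP 7.3 tabulates events leading to withdrawal from the study. SAP 8 only refers tolerability to the safety analysis.

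**The concern.** Tolerability is part of the primary objective. Sections 7.1.1, 7.1.6 and 7.1.7 all stop drug for this event, so the event and the drug action are the same. What differs is whether the patient leaves the study, and leaving is what the endpoints count. Two sites that each follow a current section of the same protocol can therefore report the same clinical course as a tolerability failure in one case and not in the other.

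The rule also decides whether scheduled suicidality assessments go on after drug is stopped. Suicidality is a named safety endpoint, and Protocol 1.4.3 cites the updated individual stopping rules as one of the added safety precautions, so sites need a single instruction here.

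**Working it through.** There is no planned figure to reproduce: the sample size has no statistical basis and all analyses are descriptive. The check is a comparison of the rules, followed by simple counts.

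**Step 1. The rules side by side (Protocol).**

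| Section | Trigger | Study drug | Study participation |
|---|---|---|---|
| 7.1.6 | AE of suicidal ideation or attempt | Stop | Leave |
| 7.1.1 | Same AE | Stop | May stay off drug |
| 7.1.7 | AE of suicidal behavior or ideation | Stop | Early termination visit, then may stay off drug |
| 3.10.1 | AE of suicidal ideation or attempt | Discontinue (drug or study not named) | May stay if drug was stopped for safety or tolerability |
| 6.1.5 | PBA-s suicidal ideation score above 2 | Stop | May stay off drug |
| 7.8.1 | C-SSRS or PBA-s ideation above 2, or a C-SSRS suicidal act | Stop | May stay off drug |

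The trigger in 7.1.6 is the trigger in 7.1.1, so the two cannot be read as rules for different events. An instruction to leave the study cannot be followed together with permission to stay in it. Sections 6.1.5 and 7.8.1 act on scores or acts rather than on the AE as such, but they too stop drug only.

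**Step 2. Effect on the endpoints.** Take a patient with this event who would stay off drug to the end of the study. Under 7.1.6 the patient adds 1 to the numerator of both tolerability proportions; under 7.1.1 the patient adds 0.

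- Shift per patient = 1/N.
- N = 300 (Protocol 9.1): 1/300 = 0.33 percentage points.
- N = 650 (SAP 2.4): 1/650 = 0.15 percentage points.

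With k such patients the shift is k/N. The documents give no incidence, so k is unknown. Both N are planned maxima; a smaller safety set makes the shift per patient larger.

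**Step 3. Scheduled suicidality contacts forgone.** Protocol Table 1 has C-SSRS with PBA-s at each visit, and C-SSRS with the abbreviated PBA-s at the week 18 and 38 calls. Contacts before the final visit at week 106:

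- removed at week 4: weeks 12, 18, 26, 38, 52, 78, 104 = 7
- removed at week 12: weeks 18, 26, 38, 52, 78, 104 = 6
- removed at week 26: weeks 38, 52, 78, 104 = 4
- removed at week 52: weeks 78, 104 = 2

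SAP 2.1 repeats the calls every 26 weeks after week 38, which adds weeks 64 and 90. Up to week 104 the counts become 7+2 = 9, 6+2 = 8, 4+2 = 6 and 2+2 = 4. All are maxima: they assume that the patient would have stayed and attended every contact.

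**The case against.** The effect on the endpoint is narrow. Staying is optional under 7.1.1, so a patient who chooses to leave is counted under either section. Section 7.1.7 also says that a patient with any adverse event "may be withdrawn from the study or from study treatment at any time at the discretion of the investigator", so the endpoint already depends on discretion for every event and 7.1.6 adds one case. No decision rule rests on the proportion. SAP 5.2 already summarises withdrawals from treatment and from study with reasons, and the all-AE table will show how many patients had the event. All of this stands, and it limits the size. It does not remove the conflict, because disposition counts do not change what the named endpoint counts and do not give events leading to drug discontinuation by SOC and PT.

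Four stronger readings are tempting and are not supported:

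- *The early termination visit shows that 7.1.7 also ends participation.* Section 3.1 does tie early termination procedures to patients who withdraw, at their final visit. But the full sentence in 7.1.7 can be read as a drug-return visit, and the section closes by letting patients stay. It is unclear rather than a second removal rule.
- *Removed patients are lost to safety follow-up.* Section 7.1.7 says: "Adverse events of suicidal behavior/ideation should be followed until resolution of the suicidal behavior/ideation". What can be lost is the scheduled scale assessments.
- *Psychiatric referral is left open.* Sections 6.1.5, 7.1.6 and 7.8.1 direct it for this event, and 7.1.1 directs immediate referral for suspected suicidality. Only one phrase in 7.1.7 is softer, and it has no bearing on the endpoint.
- *The analysed study ran under this wording.* The SAP describes a later amendment (650 patients, an internal safety committee, re-enrolment). For suicidality scores and acts, SAP 2.1 stops medication and states no exit from the study. The later text of 7.1.6 is not available.

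**Conclusion.** The conflict is certain in the protocol version supplied: 7.1.6 removes the patient from the study for an event for which 7.1.1 and 7.1.7 stop drug and allow the patient to stay, and 3.10.1 does not settle the matter. Because the tolerability endpoints and the SAP 7.3 withdrawal table count leaving the study, a patient who would have stayed is classified by the section the site happens to follow.

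The size is 0.33 points per such patient at N=300 and 0.15 at N=650, with up to 7, 6, 4 or 2 scheduled suicidality contacts forgone under Protocol Table 1 for removal at week 4, 12, 26 or 52. A reader might infer that the tolerability result is materially biased. The documents do not support that, since they give neither an incidence nor the share of patients who would stay. The conclusion is that the rule and the count should be corrected. How far the result would move is unknown.

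**What to change.** 1. **Protocol wording.** In 7.1.6, remove the instruction to discontinue the patient from the study and keep the stop of medication and the referral. In 3.10.1, state that the suicidality criteria mean discontinuation from study drug. In 7.1.7, say that patients who stay off drug return their supply at a visit and continue the scheduled visits, and that the early termination visit is only for those who leave.
2. **SAP 7.3 and 8.** Add a table of adverse events leading to permanent study drug discontinuation by SOC and PT. Report the AE tolerability proportion twice: as left study and as stopped drug. This is worth having even after the wording is aligned, because 7.1.7 leaves the choice between study and treatment withdrawal to the investigator for any event.
3. **Separate, minor safety alignment.** In 7.1.7, replace the instruction to assess the need for a psychiatric evaluation with the required referral found in 6.1.5, 7.1.6 and 7.8.1. Write it out in full, since 6.1.5 and 7.8.1 also leave referral of patients off treatment to the investigator's judgment.

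The cost is short edits to three protocol sections with a clarification to sites, one extra table and one extra line of output. No new data are needed, because Protocol 7.1.2 already records the action taken with study drug for each event. If the later amendment already corrects 7.1.6, only the parts of items 1 and 3 that it leaves open remain, together with item 2.
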